#### Part B

If the ETT Visit occurs 3 weeks or later following the last dose of study drug, then the ETT Visit will replace the Safety Follow-up Visit, and a separate Safety Follow-up Visit will not be required.

Subjects who prematurely discontinue study drug treatment will continue to complete all scheduled study visits for assessments following completion of the ETT Visit, as detailed in [Table 3-4](#).

Subjects who prematurely discontinue treatment in Part B are not eligible to enroll in the optional open-label extension safety study.

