9.4.2 Clinical Laboratory

Part A and Part B

For the treatment-emergent laboratory assessments, the observed values and change from baseline values of the continuous hematology, coagulation and chemistry results will be summarized in SI units at each visit.

The number and percentage of subjects meeting at least 1 threshold analysis criterion event for selected parameters during the TE period will be summarized. The threshold analysis criterion shift from baseline will also be summarized for selected laboratory parameters. The threshold analysis criteria are provided in [Appendix E](#).

Results of urinalysis and the positive urine/serum pregnancy test will be listed in individual subject data listings only. For positive serum pregnancy listing, subjects with serum HCG which are abnormal will be selected.

In addition, a listing containing individual subject hematology, chemistry, and coagulation values will be provided. This listing will include data from both scheduled and unscheduled visits.

Part B Only

For selected LFT laboratory tests (alanine transaminase [ALT], aspartate transaminase [AST], alkaline phosphatase [ALP], and total bilirubin), a scatter plot of the maximum treatment-emergent value versus the baseline value corresponding to \times ULN (upper limit of normal) will be presented. Further, a scatter plot of the maximum treatment-emergent value of ALT and AST, separately, versus the maximum treatment-emergent value of total bilirubin corresponding to \times ULN will also be presented.

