		Safety Follow-up	Not applicable
• Coagulation	Day 1 (Baseline)	1	≤1 Pre-dose
	Week 24	169	[1, 183]
	Safety Follow-up	Not applicable	Use nominal visit
Efficacy Assessment and Pharmacodynamic Assessment			
• Spirometry	Day 1 (Baseline)	1	≤1 Pre-dose
	Day 15	15	(1, 22]
	Week 4	29	(22, 43]
	Week 8	57	(43, 71]
	Week 12	85	(71, 99]
	Week 16	113	(99, 141]
	Week 24	169	(141, 183]
		Safety Follow-up	Not applicable

Table 12-2 Analysis Visit Windows for Safety and Efficacy Assessments in Part B			
Assessment	Visit¹	Target Study Day	Analysis Visit Window (in study days)^{2, 3, 4}

 Weight, Height and BMI (and the corresponding z-scores) 	Day 1 (Baseline)	1	≤1
	Day 15	15	(1, 22]
	Week 4	29	(22, 43]
	Week 8	57	(43, 71]
	Week 12	85	(71, 99]
	Week 16	113	(99, 141]
	Week 24	169	(141, 183]
	Safety Follow-up	Not applicable	>183

 Modified Facial Hedonic Scale 	Day 1	1	≤1
	Day 15	15	(1, 22]
	Week 4	29	(22, 43]
	Week 8	57	(43, 71]
	Week 12	85	(71, 99]
	Week 16	113	(99, 141]
	Week 24	169	(141, 183]
	Safety Follow-up	Not applicable	>183

 CFQ-R 	Day 1 (Baseline)	1	≤1
	Week 4	29	(1, 43]
	Week 8	57	(43, 71]
	Week 12	85	(71, 99]
	Week 16	113	(99, 141]
	Week 24	169	(141, 183]
	Safety Follow-up	Not applicable	>183

 Sweat Chloride Lung Clearance Index 	Day 1 (Baseline)	1	≤1 Pre-dose
	Day 15	15	(1, 22]
	Week 4	29	(22, 57]
	Week 12	85	(57, 127]
	Week 24	169	(127, 183]

Notes:

¹ Visit name for analysis purpose is used to report data in tables and figures.

² The analysis visit windows will be applied using the following rules for both scheduled and unscheduled visits:

- If no numerical measurement is available within a visit window, the measurement will be considered missing for the visit.
- If there is more than 1 numerical measurement available within a visit window, use the following rules:
 - The measurement closest to the target day will be used; or
 - If there are multiple measurements with the same distance from the target day, the latest measurement will be used. If the latest measurement cannot be determined, then unscheduled visit will be selected

³ For measurements collected on the date of first dose of study drug, if it cannot be determined whether the measurement is before or after the first dose:

- a. Scheduled measurement will be treated as pre-dose observation.
- b. Unscheduled measurement will be treated as post-dose observation.

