⁴ For safety assessment, Safety Follow-up analysis visit will be based on nominal Safety Follow-up visit. If a subject doesn't have a nominal Safety Follow-up visit but has an ETT visit with study day >29 for Part A and >183 for Part B, then the ETT visit will be mapped into Safety Follow-up analysis visit.

⁵ For efficacy analysis of Part B, if there are assessments with study days > 183, the nominal Safety Follow-up visit will be mapped to the Safety Follow-up visit. If there is only ETT assessment with study day > 183, the ETT visit will be mapped to the Safety Follow-up visit.

Derived Variables:

1. Age (in years) at first dose date and nominal visit (for demographics, listing and the calculation of [percent] predicted spirometry variables):

Obtain the age at informed consent/assent (in days) in "yy, mm" format (e.g., 24 years, 6 months) from the Vital Signs (VS) page at the Screening Visit, and add 0.5 month to convert to days.

Obtain the informed consent/assent date.

Then age (in years) at first dose or nominal visit = [(first dose date or nominal visit date – informed consent/assent date) in days + age at informed consent/assent (in days)]/365.25.

2. Age (in months) at nominal visit (for use in calculation of BMI, weight z-score and height z-score, as applicable):

Obtain the age at informed consent/assent (in months) in "yy, mm" format (e.g., 24 years, 6 months) from Vital Signs (VS) page at the Screening Visit.

Obtain the informed consent/assent date.

Then age (in months) at nominal visit = integer part of {[age at informed consent/assent (in months) + 0.5 + diff (first dose date or nominal visit date, informed consent/assent date) in months]} + 0.5.

3. Missing first dose date or last dose date

If the first dose date is missing, use Day 1 visit date to impute.

If the last dose date is missing or partial date is reported, the last dose date will be imputed based on, in descending order priority, the Early Treatment Termination (ETT) visit date, last visit date before the Safety Follow-up, or the last study drug administration date from EX SDTM domain, as appropriate. The imputation algorithm will ensure the imputed last dose date does not exceed the study participation end date.

4. Sweat Chloride:

Non-missing sweat chloride concentrations from the left arm and right arm with assessment end date/time for a given arm up to 30 minutes after first dose time in treatment period will be considered for baseline.

5. Electrocardiogram:

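### Part B early-termination (ETT) safety results are placed by study day, so an ETT coagulation value can appear as Week 24, and an ETT that replaces Safety Follow-up is mapped there only after Day 183

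*SAP*

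**What the plan says.** **Safety Follow-up mapping.** SAP Appendix A, note 4, states for safety data that "Safety Follow-up analysis visit will be based on nominal Safety Follow-up visit". If there is no such visit, an ETT is used instead, but only where the subject "has an ETT visit with study day >29 for Part A and >183 for Part B". Time since the last dose plays no part in this test.

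**Protocol 9.1.4, Part B.** The replacement rule runs on time since last dose: "If the ETT Visit occurs 3 weeks or later following the last dose of study drug", "the ETT Visit will replace the Safety Follow-up Visit, and a separate Safety Follow-up Visit will not be required". The same section says that early stoppers "will continue to complete all scheduled study visits for assessments following completion of the ETT Visit".

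**Coagulation.** Protocol Table 3-4 takes Part B coagulation at Day 1, Week 24, ETT and Safety Follow-up. SAP Table 12-2 gives it one post-baseline window before Safety Follow-up: Week 24, target Day 169, [1, 183]. There is no ETT analysis visit. Hematology's Week 24 window is (141, 183] and serum chemistry's is (155, 183]. If several results fall in one window, Appendix A, note 2, says: "The measurement closest to the target day will be used".

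**Summaries.** SAP 9.4.2 says of treatment-emergent (TE) laboratory data that "continuous hematology, coagulation and chemistry results will be summarized in SI units at each visit". Under SAP 9.1 the TE Period ends no later than 28 days after the last dose.

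**The concern.** The two documents use different tests for the same substitution. A child whose ETT replaces Safety Follow-up under the protocol has no nominal Safety Follow-up visit. If the ETT is on or before Day 183, the SAP treats it as a candidate for a scheduled-visit row, and the child is missing from the Safety Follow-up row.

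For coagulation, the Week 24 window opens on Day 1, so a sample taken after days or weeks of treatment can be printed as a 24-week value.

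Clinical laboratory values are part of the Part B primary endpoint (protocol 7.1, SAP 6.1). At stake is whether the Week 24 and Safety Follow-up rows show what their labels say.

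**Working it through.** The plan gives no figure on this point to reproduce. The check runs the SAP's rules over possible last-dose days. The counts are of last-dose days, not of expected children.

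**1. Replacing ETT and note 4**

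Inputs: the Week 24 target is Day 169 (SAP Table 12-2), and the last planned dose is the evening before that visit (protocol 9.6.1), so Day 168. Early last-dose days L therefore run from 1 to 167. The gap g between last dose and ETT is assumed, with g at least 21 days as protocol 9.1.4 requires.

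The SAP does not map the ETT when L + g ≤ 183, that is, when L ≤ 183 − g.

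| g (days) | Unmapped L | Share of 167 |
|---|---|---|
| 21 | 1 to 162 | 162/167 = 97% |
| 24 | 1 to 159 | 159/167 = 95% |
| 28 | 1 to 155 | 155/167 = 93% |
| 35 | 1 to 148 | 148/167 = 89% |

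A gap above 28 days puts the ETT outside the TE Period, so TE-limited summaries would omit it under either rule. For those summaries the relevant range is 93% to 97%.

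Example: last dose Day 30, ETT Day 51 (30 + 21). Chemistry falls in the Week 8 window (43, 71]. It is either printed as Week 8 or displaced by a result closer to Day 57. In neither case does it reach Safety Follow-up.

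**2. ETT coagulation printed as Week 24**

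Inputs: window [1, 183], target Day 169, TE limit L + 28. Assumed: L from 1 to 160; ETT 3, 7 or 21 days after last dose; Week 24 visit not attended, or attended on Day 164, 169 or 174 (the protocol's ±5 days).

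If Week 24 was not attended, the ETT is the reported Week 24 value for 160 of 160 days. If it was attended, the result depends on an order that the SAP does not state. The table counts last-dose days, out of 160, on which the ETT is the reported value:

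| Order | Gap | Week 24 on Day 164 | Day 169 | Day 174 |
|---|---|---|---|---|
| Closest record first | 3 | 0 | 0 | 0 |
| | 7 | 4 | 0 | 3 |
| | 21 | 11 | 1 (tie) | 10 |
| TE limit first | 3 | 135 | 140 | 145 |
| | 7 | 139 | 140 | 148 |
| | 21 | 146 | 141 | 153 |

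The difference arises because a Day 169 sample is inside the TE Period only if L + 28 ≥ 169, so L ≥ 141. For an earlier stopper, applying the TE limit first removes the real Week 24 sample and leaves the ETT.

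Example: last dose Day 30, ETT Day 33, Week 24 on Day 169. The TE limit is Day 58 (30 + 28). With the TE limit first, the Day 33 value is printed as Week 24. With the closest record first, Day 169 is chosen (distance 0 against 136); if the TE limit is then applied, the child has no Week 24 value.

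**3. Effect of the changes proposed below**

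- Note 4 with a 21-day test: an ETT 21 days after last dose maps for 167 of 167 days, against 5 of 167 now (L = 163 to 167).
- Coagulation window (141, 183], TE limit first, Week 24 on Day 169, 3-day gap: the ETT stays in the window only if L + 3 ≥ 142, so L ≥ 139. Days on which the ETT is printed as Week 24 fall from 140 to 2 (L = 139 and 140), and those two ETTs are on Days 142 and 143. With a 7-day gap, L ≥ 135, so they fall from 140 to 6.

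**The case against.** The case for leaving the plan alone has real force.

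- **Coagulation.** A reader might infer that every early stopper's ETT coagulation result becomes Week 24. The documents do not support that. Early stoppers are to keep attending, including Week 24, and the record nearest Day 169 is used. An ETT after Day 183 is outside the window. With the closest record chosen first, an attended Week 24 visit nearly always displaces the ETT.
- **Replacing ETTs.** Protocol 9.1.4 asks for the ETT as soon as possible after the decision to stop, so one 3 weeks or more after the last dose should be the exception. Other early stoppers who stay in the study are due a nominal Safety Follow-up visit, which the SAP uses. It would be wrong to infer that the Safety Follow-up row generally loses its off-drug values.
- **Role of the protocol rule.** Section 9.1.4 says which visit is required, not how to tabulate it. But note 4 itself lets an ETT stand in for Safety Follow-up, so the intent is shared and only the test differs.
- **Other outputs.** AE tables, threshold counts over the TE Period, maximum-value liver plots and listings do not depend on these labels. Safety analysis is descriptive, without testing.

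All four limit the point. None removes the mismatch between the two tests or explains a Week 24 window that opens on Day 1.

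**Conclusion.** The point holds for Part B only. The replacement rule is headed Part B, and Part A takes no coagulation sample at ETT (protocol Table 3-2).

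- An ETT coagulation result on or before Day 183 can be reported as Week 24 when no closer eligible result exists. That happens when Week 24 was not attended or, if the TE limit is applied first, when the real Week 24 sample falls more than 28 days after the last dose.
- A replacing ETT is not mapped to Safety Follow-up unless it is after Day 183. This covers 93% to 97% of early last-dose days for gaps of 28 to 21 days.

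The number of children affected is unknown. Planned non-completion, 56 − 45 = 11 (11/56 = 19.6%), is only a planning ceiling. It can include children who withdraw consent or are lost to follow-up and have no ETT sample. A reader might infer that the Week 24 mean change in coagulation would be diluted by about 20%. That would require all 11 to have an ETT sample, no eligible Week 24 value and no change from baseline, and the documents give none of these.

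The consequence is wrong or missing labels in by-visit descriptive summaries of a primary-endpoint component. The change is worth making because it is cheap.

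**What to change.** Three edits to SAP Appendix A:

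1. In Table 12-2, narrow the Part B coagulation Week 24 window to (141, 183] and show earlier ETT coagulation values in a separate ETT row. Hematology is the right model because, like coagulation, it has no Week 20 visit. Chemistry's (155, 183] reflects its Week 20 visit and would drop Day 142 to 155 samples for no stated reason.
2. In note 4, for Part B, map an ETT to Safety Follow-up when there is no nominal Safety Follow-up visit and the ETT is at least 21 days after the last dose, as in protocol 9.1.4. Remove that ETT from the scheduled-visit rows.
3. State whether the TE limit is applied before or after the closest record is chosen.

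Edit 2 alone is not enough: an ETT less than 21 days after the last dose would still fall in the coagulation Week 24 window. No new data are needed. The cost is a slightly smaller n in the Week 24 coagulation row.

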### 9.1.4 Early Termination of Treatment

#### Parts A and B

If a subject prematurely discontinues study drug treatment, an Early Termination of Treatment (ETT) Visit should be scheduled as soon as possible after the decision to discontinue treatment. Subjects who prematurely discontinue treatment will also be required to complete the Safety Follow-up Visit ([Table 3-2](#) for Part A and [Table 3-4](#) for Part B), if applicable (Section 9.1.3).

If a subject withdraws from the study and also withdraws consent or assent, no further assessments will be performed. Vertex may retain and continue to use any data and samples collected before such withdrawal of consent or assent.

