9 STATISTICAL ANALYSIS

9.1 General Considerations

Part A and Part B

Data from Part A and Part B will be analyzed separately.

The Schedule of Assessments is provided in Section 3 of the CSP. The precision standards for reporting safety and efficacy variables are provided in an internal Biometrics document that specifies the programming rules including the precision for derived variables.

Continuous variables will be summarized using the following descriptive summary statistics: the number of subjects (n), mean, standard deviation (SD), median, minimum value (min), and maximum value (max).

Categorical variables will be summarized using counts and percentages. Percentages will be presented to 1 decimal place.

Baseline unless otherwise specified, is defined as the most recent non-missing measurement (scheduled or unscheduled) collected prior to the first dose of study drug in the corresponding Part.

Note: for subjects who take Orkambi or Symdeko (branded as Symkevi in Europe) during the 28 days before the screening visit, the data collected at screening visit will not be used for baseline derivation for spirometry, sweat chloride and LCI.

Absolute change from baseline will be calculated as Post-baseline value – Baseline value.

Relative change from baseline will be calculated and expressed in percentage as 100% × (Post-baseline value – Baseline value) / Baseline value.

Treatment-emergent (TE) Period for Part A and Part B will include the time from the first dose of study drug in the corresponding Part through 28 days after the last dose or the completion of study participation date in the corresponding Part, whichever occurs first.

Extended Treatment-emergent (TE) Period for Part B will include the time from the first dose of study drug in Part B through the completion of study participation.

For subjects who do not have unscheduled visit after the Week 24 visit, refer to Section 9.1.6 of the CSP for the definition of completion of study participation. For subjects who have unscheduled visit after the Week 24 visit, the completion of study participation is defined as the date of the last unscheduled visit.

Unscheduled visits: Unscheduled visit measurements will be included in analysis as follows:

- In scheduled visit windows per specified visit windowing rules

- In the derivation of baseline and last on-treatment measurements

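### SAP Appendix A imputes a partial last-dose date as if it were missing, ETT visit date first, so a reported month can be overwritten and exposure and the end of the Part B TE Period can run late

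*SAP*

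**What the plan says.** The rule in SAP Appendix A, Derived Variables 3 has one trigger for two situations: "If the last dose date is missing or partial date is reported". In both, "the last dose date will be imputed based on, in descending order priority, the Early Treatment Termination (ETT) visit date". Next in line are the "last visit date before the Safety Follow-up, or the last study drug administration date from EX SDTM domain, as appropriate". The single stated limit is this: "The imputation algorithm will ensure the imputed last dose date does not exceed the study participation end date". Nothing says that a reported month or year is kept.

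The other date rules in the SAP do use what was reported. Appendix B completes a medication stop date that lacks only the day with the last day of that month. Appendix D builds adverse event start dates from the reported month and year, and closes a partial end date at the end of the reported month or at the end of participation, whichever is earlier.

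On timing, protocol 9.1.4 says that the ETT Visit "should be scheduled as soon as possible after the decision to discontinue treatment". For Part B it also provides for a long delay: "If the ETT Visit occurs 3 weeks or later following the last dose of study drug", the ETT Visit takes the place of the Safety Follow-up Visit.

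The last-dose date feeds exposure (SAP 9.2.5), compliance and percentage of tablets taken (SAP 9.2.6) and the TE Period, which runs "through 28 days after the last dose or the completion of study participation date", whichever comes first (SAP 9.1).

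**The concern.** A partial date carries information. If a site records the last dose as some day in March and the ETT Visit is on 20 April, the rule as written returns 20 April. The latest date that agrees with the record is 31 March, so the imputed date is at least 20 days late and contradicts the site's entry.

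The error runs in one direction whenever the ETT Visit falls after the last dose. It lengthens exposure, enlarges the denominator of tablets taken, and can bring events that began more than 28 days after stopping into the TE Period. Part B safety, the primary objective, is summarised over that period. The children concerned are those who stopped early, whose exposure and events will be read most closely.

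**Working it through.** The documents attach no figure to this rule, so there is none to reproduce. The check applies the SAP's own definitions.

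**Inputs**
- Exposure = last dose date − first dose date + 1 (SAP 9.2.5).
- TE end = the earlier of last dose + 28 days and completion of participation (SAP 9.1).
- Completion for a Part B discontinuer who does not withdraw consent = the latest of the Week 24, ETT or (if required) Safety Follow-up Visit (protocol 9.1.6).
- Assumed, because the documents give no distribution: the true last-dose day; the gap g from last dose to ETT; Week 24 Visit on Day 169; Safety Follow-up 28 days after the last dose unless an ETT Visit at 21 days or later replaces it; the child stays in follow-up.

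**Effect when the ETT date replaces the true date**

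Imputed exposure = true exposure + g, so the relative error is g divided by true exposure.

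| True last dose | g (days) | Exposure, true → imputed | Error | TE end, true → imputed | Shift |
|---|---|---|---|---|---|
| Day 40 | 21 | 40 → 61 | +52.5% | 68 → 89 | +21 |
| Day 57 | 7 | 57 → 64 | +12% | 85 → 92 | +7 |
| Day 57 | 21 | 57 → 78 | +37% | 85 → 106 | +21 |
| Day 57 | 28 | 57 → 85 | +49% | 85 → 113 | +28 |
| Day 120 | 21 | 120 → 141 | +17.5% | 148 → 169 | +21 |
| Day 120 | 28 | 120 → 148 | +23.3% | 148 → 169 (capped) | +21 |
| Day 150 | 7 | 150 → 157 | +4.7% | 178 → 178 (capped) | 0 |

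**Where the cap removes the TE shift**
- A child with last dose on Day 57 whose participation ends at an ETT Visit 21 days later has a TE end of Day 78 either way: min(85, 78) = min(106, 78) = 78.
- Part A discontinuers: no shift if Safety Follow-up is 21 or 28 days after the last dose. If it is at 35 days, the shift is at most 35 − 28 = 7 days.
- Part B completers have no ETT Visit, so the Week 24 Visit is the source. The last dose is the evening before (protocol 9.6.1), so exposure is 1 day too long and the TE end moves 0 or 1 day. With Week 24 on Day 169, true exposure is 168/7 = 24.0 weeks, and the extra day moves the child into the category above 24 weeks.

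**Compliance measures.** A child who took every tablet through Day 57 and has g = 21 shows 57/78 = 73% of tablets taken, below the 80% cut used in the compliance summary. Interruption-based compliance moves the other way, since the same interruption days are divided by a longer duration.

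**How often the month would change.** If the last dose is spread evenly over a month of 30.4 days (assumption), the ETT date falls in a later month with probability g/30.4: 23% at g = 7, 46% at g = 14 and 69% at g = 21.

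**Weight in the study total.** One child with 21 extra days, against 45 completers at 168 days, adds 21/(45 × 168) = 0.28% to total exposure.

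**The case against.** The strongest defence is that little depends on this rule. Missing and discrepant data are queried with the investigator (protocol 13.3), so few partial dates should remain, and the words "or the last study drug administration date from EX SDTM domain, as appropriate" leave room for judgement. Adverse events are reported as counts and percentages of subjects without testing, and the SAP plans no exposure-adjusted event rate for extra days to dilute. A later TE end captures more events, in keeping with the SAP's default of treating events of uncertain date as treatment-emergent. The Part B Extended TE Period does not depend on the last-dose date, and all adverse events are listed. This stands as a limit on importance. It does not justify replacing a reported month: unspecified discretion is no rule, and overstated exposure is not conservative.

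A reader might infer several stronger points that the documents do not support.
- *The recorded dosing date should rank first.* Part B requires dates and times of dosing to be recorded for the 2 days before and the day of PK sampling (protocol 9.6.1). If EX holds mainly those records, its last date could fall well before the true last dose.
- *Drug-accountability dates would be better.* Protocol 10.4 covers drug received, dispensed and returned; none of these is a dosing date.
- *The second choice is always late.* Only the Week 24 Visit has no site dose. At Day 15 and Weeks 4, 8, 12 and 16 the morning dose is given at the site, so for a child who then disappears that date may be exact or early.
- *The ETT Visit is routinely 3 weeks late, or is never a dosing day.* The 3-week gap is a contingency, and nothing excludes a last dose on the ETT day, when the error is nil.
- *The whole TE Period shifts.* Only its end moves.

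**Conclusion.** The point holds for partial dates. As written, Derived Variables 3 can move the last dose into a later month than the one reported, which Appendices B and D avoid for their own dates. Exposure and the tablets-taken denominator are overstated by the full gap. The Part B TE Period ends later by up to that gap, limited by completion of participation: the full gap for early discontinuers who remain in follow-up, little or nothing for late discontinuers, completers and most of Part A.

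The percentages rest on assumed last-dose days and gaps. That a known month is overridden follows from the wording but is not stated outright. The number of children affected cannot be derived from the documents and is probably very small. This is a minor correction, worthwhile because the present rule can contradict recorded data and the remedy is cheap. The documents do not support reordering the sources for a fully missing date.

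**What to change.** Amend SAP Appendix A, Derived Variables 3 as follows.

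1. **Partial date:** keep the reported month and year and impute the last day consistent with them, no later than the ETT Visit (or the day before the Week 24 Visit for completers) and no earlier than the last administration recorded in EX.
2. **Fully missing date:** keep the present order of sources, but require the imputed date to be no earlier than the last recorded administration, and use the day before the Week 24 Visit where that visit is the source.
3. Keep the existing cap at the end of participation, and flag imputed dates in the listing.

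For a partial date with only the day missing, the remaining error cannot exceed 30 days, cannot cross into a later month, and cannot exceed the error of the present rule, because the imputed date is never after the ETT Visit.

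The cost is a few sentences, one derivation and a listing flag. The downside is a slightly shorter TE Period for the few imputed children; their later events stay in the Extended TE Period where it applies (Part B) and in the listings.
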